3.2 Number of Sites

Approximately 50 centers in Japan will participate in the study. Sites that do not enroll subjects within 3 months of site initiation may be closed.

3.3 Number of Subjects

Participants in this clinical investigation shall be referred to as “subjects”.

Approximately 80 Japanese subjects with chronic stable HF with reduced ejection fraction will be enrolled.

Rationale for the sample size can be found in [Section 10.2](#).

3.4 Replacement of Subjects

Subjects who are withdrawn, removed from treatment or the study, or who voluntarily withdraw prematurely from the study will not be replaced.

3.5 Estimated Study Duration

3.5.1 Study Duration for Subjects

After signing the informed consent, all eligible subjects should be randomized within 30 days. Treatment duration will be for 16 weeks with the EOS visit at week 20 for a maximal duration of study participation of approximately 24 weeks or 6 months (includes screening, treatment period, and EOS visit).

3.5.2 End of Study

The end of the study is defined as the last day on which the last randomized subject in this study completes the assessments for end-of-study visit (week 20) or terminates the study early.

4. SUBJECT ELIGIBILITY

Investigators will be expected to maintain a screening log of all potential study candidates that includes limited information about the potential candidate (eg, date of screening).

Before any study-specific activities/procedure, the appropriate written informed consent must be obtained (see [Section 11.1](#)).

4.1 Inclusion and Exclusion Criteria

4.1.1 Inclusion Criteria

- 101 Subject or their legally authorized representative has provided written informed consent prior to initiation of any study-specific activities/procedures
- 102 Japanese male or female ≥ 20 years and ≤ 85 years of age at the time of written informed consent
- 103 History of chronic stable HF with reduced ejection fraction, defined as requiring treatment for HF for a minimum of 4 weeks prior to screening
- 104 Treated for HF with optimal pharmacological therapy. In general, optimal treatment will include a beta-blocker and either an ACE inhibitor or an ARB that is expected to remain stable over the period of participation in the study, unless not tolerated
- 105 LVEF $\leq 40\%$ by centrally read screening echocardiogram

4.1.2 Exclusion Criteria

- 201 Implantation of CRT or ICD implantation within 30 days prior to randomization
- 202 NYHA class IV
- 203 Likely to receive within 3 months after randomization, in the opinion of the investigator, revascularization, implantation of ICD or CRT, ventricular assist device, continuous or intermittent inotropic therapy, hospice care, or cardiac transplant
- 204 Severe uncorrected valvular heart disease
- 205 Hypertrophic obstructive cardiomyopathy, active myocarditis, or constrictive pericarditis, or clinically significant congenital heart disease
- 206 Acute myocardial infarction, unstable angina, or persistent angina at rest within 30 days prior to randomization
- 207 Chronic antiarrhythmic therapy, with the exception of amiodarone, digoxin and beta-blocker therapy
- 208 Routinely scheduled outpatient IV infusions for HF (eg, inotropes, vasodilators [eg, carperitide], diuretics) or routinely scheduled ultrafiltration
- 209 Systolic BP > 160 mm Hg or < 90 mm Hg, or diastolic BP > 90 mm Hg, or HR > 110 beats per minute (bpm) or HR < 50 bpm at screening
- 210 Estimated glomerular filtration rate (eGFR) < 30 mL/min/1.73m² by central laboratory during screening
- 211 Currently taking, or has taken within 14 days prior to randomization, a potent CYP3A4 inhibitor (amprenavir, cobicistat, cyclosporine, clarithromycin, delavirdine, erythromycin, indinavir, itraconazole, nelfinavir, ritonavir, saquinavir, telaprevir, verapamil, voriconazole, grapefruit juice)
- 212 Currently taking, or has taken within 28 days prior to randomization, a potent CYP3A4 inducer (eg, carbamazepine, dexamethasone, efavirenz, etravirine, nevirapine, phenobarbital, phenytoin, rifabutin, rifampicin, St. John's wort)
- 213 Severe, concomitant noncardiovascular disease that is expected to reduce life expectancy to less than 1 year
- 214 Past recipient of any major organ transplant (eg, lung, liver, heart, bone marrow, renal) or receiving renal replacement therapy by dialysis
- 215 Malignancy within 1 year prior to randomization with the following exceptions: localized basal or squamous cell carcinoma of the skin or cervical intraepithelial neoplasia
- 216 Known untreated hypothyroidism or hyperthyroidism, adrenal insufficiency, active vasculitis due to collagen vascular disease
- 217 Hepatic impairment defined by a total bilirubin (TBL) \geq 2 times the upper limit of normal (ULN), or alanine aminotransferase (ALT) or aspartate aminotransferase (AST) \geq 3 times ULN by central laboratory during screening
- 218 Any acute or serious co-morbid condition (eg, major infection or hematologic, renal, metabolic, gastrointestinal or endocrine dysfunction, major arrhythmia) that, in the judgment of the investigator, could lead to premature termination of study participation or interfere with the measurement of, or the interpretation of, the efficacy and safety assessments in the study

- 219 Previously received omecamtiv mecarbil
- 220 Currently receiving treatment in another investigational device or drug study, or less than 30 days since ending treatment on another investigational device or drug study(s)
- 221 Recent (within 3 months) history of alcohol or illicit drug abuse based on self-report
- 222 Female subject is pregnant or breastfeeding or is planning to become pregnant during treatment with IP (omecamtiv mecarbil or placebo) and within 5 days after the end of treatment with IP
- 223 Female subject of childbearing potential who is not willing to inform her partner of her participation in this clinical study and to use two (2) acceptable methods of effective birth control or practice sexual abstinence or surgical contraceptive methods (vasectomy [male partner] or bilateral tubal ligation/occlusion) during treatment with IP (omecamtiv mecarbil or placebo) and for an additional 5 days after the last dose of IP
- A female is considered of childbearing potential unless permanently sterilized (she has had a hysterectomy, bilateral oophorectomy, or bilateral salpingectomy or she is postmenopausal). Menopause is defined as: age \geq 55 years with cessation of menses for 12 or more months; age < 55 years but no spontaneous menses for at least 2 years; age < 55 years and spontaneous menses within the past 1 year, but currently amenorrheic (spontaneous), AND with postmenopausal gonadotropin levels (luteinizing hormone (LH) and follicle-stimulating hormone levels (FSH) $>$ 40 IU/L) or postmenopausal estradiol levels ($<$ 5 ng/dL) or according to the definition of "postmenopausal range" for the laboratory involved.
 - acceptable methods of effective birth control include the following combinations:

intrauterine device and hormonal birth control method, or intrauterine device and barrier method with spermicide, or intrauterine hormonal-releasing system and barrier method with spermicide, or hormonal birth control method and barrier method with spermicide, or two (2) barrier methods (one by each partner) with spermicide (the male partner must use a male condom and the female must use a diaphragm)
- Note: **spermicides and diaphragm are not approved for use in Japan. If additional medications are given during treatment which may alter the contraceptive requirements (these additional medications may require a change in the type and/or length of time that contraception is to be utilized or length of time that breastfeeding is to be avoided) the investigator is to discuss these changes with the study subject.***
- 224 Known sensitivity to any of the products to be administered during dosing

- 225 Subject not likely to be available to complete all protocol-required study visits or procedures, and/or to comply with all required study procedures, to the best of the subject and investigator's knowledge
- 226 History or evidence of any other clinically significant disorder, condition or disease (with the exception of those outlined above) that, in the opinion of the investigator or Amgen physician, if consulted, would pose a risk to subject safety or interfere with the study evaluation, procedures or completion

5. SUBJECT ENROLLMENT

Before subjects begin participation in any study-specific activities/procedures, Amgen requires a copy of the site's written Institutional Review Board (IRB)/Independent Ethics Committee (IEC) approval of the protocol, informed consent form, and all other subject information and/or recruitment material, if applicable (see [Section 11.2](#)). All subjects or their legally authorized representative must personally sign and date the informed consent form before commencement of study-specific activities/procedures.

A subject is considered enrolled upon randomization in IVRS/IWRS. The investigator is to document this decision and date, in the subject's medical record and in/on the enrollment electronic case report form (eCRF). Randomization will be stratified by presence or absence of atrial fibrillation/flutter via IVRS/IWRS.

All subjects who enter into the screening period for the study (defined as the point at which the subject or legal representative signs the informed consent) will receive a unique subject identification number before any study-related activities/procedures are performed. The subject identification number will be assigned by IVRS/IWRS. This number will be used to identify the subject throughout the clinical study and must be used on all study documentation related to that subject.

The subject identification number must remain constant throughout the entire clinical study; it must not be changed after initial assignment, including if a subject is rescreened. This number will not necessarily be the same as the randomization number assigned for the study.

5.1 Randomization/Treatment Assignment

Subjects will be randomized in a 1:1:1:1 manner to receive either 25 mg BID omecamtiv mecarbil dose (n=20), 37.5 mg BID omecamtiv mecarbil dose (n=20), 50 mg BID omecamtiv mecarbil dose (n=20) or placebo (n=20) on an outpatient basis. Subjects randomized to 37.5 mg BID target dose and 50 mg BID target dose will initiate administration at 25 mg BID and will be up-titrated to the 37.5 mg BID or 50 mg BID target dose at the week 4 visit based on steady state $C_{predose}$ result from week 2.

Approved

Subjects who do not have a week 2 PK value in time for dose adjustment at the week 4 visit will be up-titrated at week 8 based on steady state $C_{predose}$ result from week 2, if available. Subjects will be up-titrated at the week 4 or week 8 visit only if the week 2 $C_{predose}$ is < 200 ng/mL. Subjects with a week 2 $C_{predose} \geq 200$ ng/mL (or not available at week 8) will continue at 25 mg BID for the remainder of the study. Subjects randomized to placebo or to 25 mg BID will receive the assigned IP throughout the study. To maintain blinding, all subjects will receive new IP supply at week 4 and week 8 visits. There is no other dose adjustment for individual subjects during the study.

Assignment to the treatment arms will be based on a computer-generated randomization schedule prepared by Amgen before the start of the study. A subject may only receive one randomization number and each randomization number will only be assigned to 1 subject.

Once eligibility into the study has been confirmed, a site representative will make the randomization call to the IVRS/IWRS to assign a randomization number to the subject. The randomization call to the IVRS/IWRS is accomplished by entering the pertinent information detailed in the IVRS/IWRS user manual. A confirmation will be sent to the site to verify that the correct information has been entered and to confirm the randomization assigned. A subject will be considered enrolled and randomized into the study when a randomization number is assigned.

5.2 Site Personnel Access to Individual Treatment Assignments

A subject's treatment assignment should only be unblinded when knowledge of the treatment is essential for the further management of a subject on this study. Unblinding at the study site for any other reason will be considered a protocol deviation. The investigator is strongly encouraged to contact the appropriate Amgen study contact representative before unblinding any subject's treatment assignment, but must do so within 1 working day after the event.

6. TREATMENT PROCEDURES

6.1 Classification of Product(s) and/or Medical Device(s)

The Amgen Investigational Product and/or placebo (IP) used in this study includes: omecamtiv mecarbil and placebo. No investigational medical devices are used in this study.

The Investigational Product Instruction Manual (IPIM), a document external to this protocol, contains detailed information regarding the storage, destruction, and administration of omecamtiv mecarbil and placebo.

6.2 Investigational Product

6.2.1 Amgen Investigational Product (Omeamtiv Mecarbil)

Omeamtiv mecarbil will be manufactured and packaged by Amgen Inc. and distributed using Amgen clinical study drug distribution procedures. Omeamtiv mecarbil will be presented as tablets in individually labeled 35ct bottles. Each bottle will have an unique bottle number.

Further details regarding IP storage condition, dispensation, packaging, labeling, accounting procedures, and destruction are outlined in the IPIM.

Placebo will be presented in identical containers and stored/packaged the same as omeamtiv mecarbil.

6.2.1.1 Dosage, Administration, and Schedule

Eligible outpatient subjects will be randomized and will initiate administration of IP (omeamtiv mecarbil or placebo). Day 1 is defined as the calendar day when treatment with IP is initiated. The first administration of IP should be on the day of randomization but not later than 5 calendar days after randomization. The time when ingestion of the first dose of IP is completed is defined as Time = 0 hours. Baseline procedures must be completed before initiation of IP and can be performed on the same day.

IP will be administered orally BID in the morning and evening by the subjects and can be taken under fasted or fed conditions. IP will be swallowed whole (not chewed) and taken with water as instructed in the IPIM. Administration of each morning and evening dose is to be taken at approximately the same time of day (12 ± 3 hours from the most recent previous dose). If IP cannot be taken or has not been taken within this window, the dose should be recorded as missed and the next dose should be taken at the regular time.

Administration of IP will start with the morning dose on day 1 and will end with the morning dose on the day of the subject's week 16 visit. The quantity, date and time, lot number, and bottle number of investigational product is to be recorded on each subject's eCRF.

6.2.1.2 Rules for Withholding Investigational Product due to Myocardial Ischemia or Infarction, Abnormal Blood Pressure or Heart Rate

Omecamtiv mecarbil may result in signs and symptoms of myocardial ischemia or infarction, as described in Section 7.1 of the Investigator's Brochure (eg, increases in HR, dizziness, dyspnea, hypotension, chest discomfort or pain, ST-segment depression on ECG, and/or elevations in troponin I or T). If a subject reports clinical signs or symptoms suggestive of myocardial ischemia or infarction, and/or experiences changes in BP or HR, withholding of IP should be considered. No antidote to omecamtiv mecarbil exists. Standard medical therapies should be used in the presence of signs or symptoms of myocardial ischemia.

The following are mandatory rules for withholding IP:

- The subject experiences clinical signs or symptoms, including ECG changes, consistent with myocardial ischemia or infarction as determined by the investigator
- The subject experiences a symptomatic decrease in systolic BP on 2 successive measurements
- The subject experiences an asymptomatic decrease in systolic BP to < 80 mmHg (measured at 3 successive timepoints over approximately 15 minutes)
- The subject experiences symptoms associated with a HR > 120 bpm, systolic BP > 170 mm Hg, or diastolic BP > 110 mm Hg that are determined by the investigator to warrant termination of the dosing
- The subject experiences sustained systolic BP > 170 mm Hg (measured at 3 successive timepoints over approximately 15 minutes)
- The subject experiences a sustained diastolic BP > 110 mm Hg (measured at 3 successive timepoints over approximately 15 minutes)
- The subject experiences a sustained HR > 120 bpm (measured at 3 successive timepoints over approximately 15 minutes)
- The subject experiences a sustained (measured at 3 successive timepoints over at least 15 minutes) HR increase ≥ 25 bpm from screening or baseline AND HR > 100 bpm

If suspected adverse drug reactions or changes in vital signs, ECGs, or clinical laboratory results are observed during the study and, in the opinion of either the investigator or the Study Medical Monitor, these changes pose a significant health risk, dosing of an individual subject should be stopped and not resumed.

If administration of IP is stopped (up to 5 days after last IP) for any of the reasons above, a blood sample of 5 mL for PK analysis is to be collected as soon as possible .

If a subject experiences clinical signs or symptoms consistent with myocardial ischemia or infarction, the subject should receive immediate medical attention according to the

institution's usual standard of care. Serial cardiac troponin samples (troponin I or T) should be analyzed at the local laboratory. In addition, central laboratory analysis of serial samples for cardiac troponin I and/or creatine kinase MB fraction (CK-MB) as well as serial 12-lead ECGs should be collected. The investigator must notify Amgen immediately of any subject experiencing clinical signs or symptoms of myocardial ischemia or infarction.

The decision to rechallenge the subject should be discussed and agreed upon unanimously by the subject, investigator, and Amgen. If signs or symptoms recur with rechallenge, then omecamtiv mecarbil should be permanently discontinued.

6.3 Hepatotoxicity Stopping and Rechallenge Rules

Subjects with abnormal hepatic laboratory values during the study (ie, alkaline phosphatase [ALP], AST, ALT, TBL) and/or international normalized ratio (INR) and/or signs/symptoms of hepatitis (as described below) may meet the criteria for withholding or permanent discontinuation of Amgen investigational product or other protocol-required therapies as specified in the [Guidance for Industry Drug-Induced Liver Injury: Premarketing Clinical Evaluation](#), U.S. Department of Health and Human Services Food and Drug Administration, July 2009.

6.3.1 Criteria for Permanent Discontinuation of Omecamtiv Mecarbil due to Potential Hepatotoxicity

Omecamtiv mecarbil should be discontinued permanently and the subject should be followed according to the recommendations in [Appendix A](#) (Additional Safety Assessment Information) for possible drug-induced liver injury (DILI), if ALL of the criteria below are met:

- TBL > 2x ULN or INR > 1.5
- AND increased AST or ALT from the relevant baseline value as specified below:

Baseline AST or ALT value	AST or ALT elevation
< ULN	> 3x ULN

- AND no other cause for the combination of the above laboratory abnormalities is immediately apparent; important alternative causes for elevated AST/ALT and/or TBL values include, but are not limited to:
 - Hepatobiliary tract disease
 - Viral hepatitis (eg, Hepatitis A/B/C/D/E, Epstein-Barr Virus, cytomegalovirus, Herpes Simplex Virus, Varicella, toxoplasmosis, and Parvovirus)
 - Right sided HF, hypotension or any cause of hypoxia to the liver causing ischemia.

- Exposure to hepatotoxic agents/drugs or hepatotoxins, including herbal and dietary supplements, plants and mushrooms
- Heritable disorders causing impaired glucuronidation (eg, Gilbert's Syndrome, Crigler-Najjar syndrome) and drugs that inhibit bilirubin glucuronidation (eg, indinavir, atazanavir)
- Alpha-one antitrypsin deficiency
- Alcoholic hepatitis
- Autoimmune hepatitis
- Wilson's disease and hemochromatosis
- Nonalcoholic Fatty Liver Disease including Steatohepatitis (NASH)
- Non-hepatic causes (eg, rhabdomyolysis, hemolysis)

If an alternative cause for hepatotoxicity is identified or less stringent conditions developed than what are noted above, the investigator should determine (based on patient population and/or severity of the hepatotoxicity or event) if Amgen investigational product and other protocol-required therapies should be withheld or permanently discontinued, as deemed appropriate for the safety of the subject, and Amgen medical monitor should be contacted immediately.

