6.3.2 Criteria for Conditional Withholding of Omecamtiv Mecarbil due to Potential Hepatotoxicity

For subjects who do not meet the criteria for permanent withholding of IP outlined above, omecamtiv mecarbil should be withheld if ANY of the following criteria are met, and the subject should be evaluated for DILI:

- Elevation of either AST or ALT according to the following schedule:

Baseline AST or ALT value	AST or ALT elevation
Any	> 8x ULN at any time
Any	> 5x ULN but < 8x ULN for \geq 2 weeks
Any	> 5x ULN but < 8x ULN and unable to adhere to enhanced monitoring schedule
Any	> 3x ULN with clinical signs or symptoms that are consistent with hepatitis (such as right upper quadrant pain/tenderness, fever, nausea, vomiting, jaundice).

- Or: TBL > 3x ULN at any time
- Or: ALP > 8x ULN at any time

Omecamtiv mecarbil should be withheld pending investigation into alternative causes of DILI. If investigational product(s) is withheld, the subject is to be followed according to recommendations in [Appendix A](#) for possible DILI. Rechallenge may be considered if an

alternative cause for impaired liver tests (ALT, AST, ALP) and/or elevated TBL is discovered, and the laboratory abnormalities resolve to normal or baseline ([Section 6.3.3](#)).

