7. STUDY PROCEDURES

7.1 Schedule of Assessments

Table 2. Schedule of Assessments

Timepoint - Day/Week/Month (window)*	Screen	D1	D7	W2 D15 (-3)	W4 D28 (+3)	D34 (+3)	W8 D56 (±3)	D62 (+3)	W12 D84 (±3)	W16 D112 (±3)	W20 ^a D140(+3) EOS
General Procedures											
Informed consent	X										
Medical history and demographics	X										
Vital Signs (HR, BP)	X	X ^c		X	X		X ^j		X	X ^k	X
AEs/SAEs/PEPs ^b	X	X		X	X		X		X	X	X
AEs/SAEs and IP compliance verification by phone or other contact			X			X		X			
Concomitant therapy	X	X		X	X		X		X	X	X
Physical examination	X										X
Body height		X									
Body weight		X		X			X		X	X	X
ECG	X	X ^c		X	X		X ^d		X	X ^d	X
Echocardiogram	X						X ^j			X ^k	
Central Laboratory											
PK samples ^e		X ^c		X ^c	X ^c		X ^j		X ^c	X ^k	
Chemistry (including eGFR at screening)	X			X			X		X	X	X
Hematology	X			X			X		X	X	X
Urinalysis		X					X				X
Troponin I, CK-MB ^e		X ^c		X	X		X		X	X	X
NT-proBNP		X ^c			X		X			X	
Samples for Development Therapeutic Monitoring Assay					X				X		
Serum pregnancy, FSH/LH or estradiol ^f	X										X
Digoxin sample (in subjects receiving digoxin)		X		X							
Investigational Product^g											
IP dispensation and/or administration at site		X		X	X		X		X	X ^h	
IP diary dispensation or collection ⁱ		X								X	
IP reconciliation (tablet count)				X	X		X		X	X	

Footnotes displayed on the next page of the Table

AE = adverse event; BP = blood pressure; CK-MB = creatine kinase-MB; ECG = electrocardiogram; eGFR = estimated glomerular filtration rate; EOS = end of study; HR = heart rate; IP = investigational product; NT-proBNP = N-terminal pro-B-type natriuretic peptide; NYHA = New York Heart Association; PEP = potential endpoint; PK = pharmacokinetic; SAE = serious adverse event.

Please note: vital signs, ECGs, and laboratory samples can be collected at any time during the study visit, unless otherwise specified below.

Visit Windows: For week 2 visit, the visit date could be 3 days prior to the scheduled date of W2; for week 4 visit, the visit date could be 3 days after the scheduled date of W4; for weeks 8, 12, and 16, the visit dates could be 3 days prior to or after the scheduled date of W8, W12, and W16, respectively; for week 20 visit (EOS), the visit date could be up to 3 days after the scheduled date of W20. The Day 34 and 62 telephone calls could be 3 days after the scheduled date of contact.

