7.4 Treatment Period

Adverse events, serious adverse events, PEPs, and concomitant medications, will be reported until EOS at week 20. If a subject is not seen at the study site, adverse events/serious adverse events/PEPs should be collected by phone. For details on reporting of adverse events and serious adverse events, please refer to [Section 9](#).

The following procedures will be completed during the study at the times designated in the Schedule of Assessments ([Table 2](#)).

- Vital signs (HR, BP)
- Adverse events/serious adverse events/PEPs, if applicable
- Concomitant therapy
- Body height, at Day 1 visit only
- Body weight, at Day 1, weeks 2, 8, 12, and 16
- ECG (centrally read), at Day 1, weeks 2, 8, 12, and 16
- Echocardiogram, at weeks 8 and 16 (centrally read)
- Blood samples for chemistry and hematology, at weeks 2, 8, 12, and 16
- Blood samples for digoxin levels (only in subjects taking digoxin), at Day 1 and week 2
- PK sample collection, at Day 1, weeks 2, 4, 8, 12, and 16
- Urine sample for urinalysis, at Day 1 and week 8
- Blood samples for troponin I, CK-MB, at Day 1 and weeks 2, 8, 12, and 16
- NT-proBNP, at Day 1, and weeks 4, 8, and 16
- Therapeutic Monitoring Assay sample collection at weeks 4 and 12
- IP dosing on site, at Day 1, weeks 2, 4, 8, 12, and 16
- IP dispensation, at Day 1, week 4 and week 8
- IP reconciliation (tablet count) at weeks 2, 4, 8, 12, and 16
- Diary dispensation, Day 1
- Return diary, week 16

7.4.1 Telephone Contact Days 7, 34, and 62

- AEs/SAEs and IP compliance will be verified by phone or other contact

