6.2 Demographics and Baseline Related Definitions

Age

Age will be calculated as the subject's age in years at enrollment as recorded on the eCRF.

Baseline ECG

For ECG, the baseline value is defined as the mean over all non-missing triplicate averages of 3 (or all available) readings from each set of triplicate taken prior to or on Study Day 1.

Other Baseline Values

For all other variables, the baseline value is defined as the last non-missing value collected prior to or on Study Day 1.

Change from Baseline

The arithmetic difference between a post-baseline value and baseline for a given time point:

Change from baseline = (post-baseline value – baseline value).

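### As printed, the permanent liver-stop rule in Protocol 6.3.1 has no AST/ALT threshold for subjects whose enzymes are both at or above ULN at baseline, although such subjects are eligible

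*Protocol*

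**What the plan says.** **Permanent stop (Protocol 6.3.1).** All of the following must hold: TBL above 2x ULN or INR above 1.5; the enzyme criterion, "AND increased AST or ALT from the relevant baseline value as specified below"; and no other immediately apparent cause. The printed table has one row, for baseline below ULN, with a threshold of more than 3x ULN. The closing paragraph adds that if another cause is identified, or "less stringent conditions developed than what are noted above, the investigator should determine" whether to withhold or permanently discontinue, and the medical monitor is to be contacted at once.

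**Conditional withholding (6.3.2).** All four AST/ALT rows apply to any baseline:
- above 8x ULN;
- above 5x but below 8x ULN for at least 2 weeks;
- the same range in a subject who cannot keep to enhanced monitoring;
- above 3x ULN with signs or symptoms of hepatitis.

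TBL above 3x ULN or ALP above 8x ULN also triggers withholding. The stated condition for a possible rechallenge is: "alternative cause for impaired liver tests (ALT, AST, ALP) and/or elevated TBL is discovered, and the laboratory abnormalities resolve to normal or baseline".

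**Rechallenge (6.3.3).** Subject, investigator and sponsor must agree unanimously. Rechallenge is ruled out absolutely only for subjects who clearly meet 6.3.1.

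**Eligibility (4.1.2, exclusion 217).** AST or ALT is disqualifying only from "3 times ULN by central laboratory during screening".

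**Baseline.** Table 2 schedules "Chemistry (including eGFR at screening") at screening and not on Day 1. Section 7.4 lists "Blood samples for chemistry and hematology, at weeks 2, 8, 12, and 16". In SAP Section 6.2, for variables other than ECG, "the baseline value is defined as the last non-missing value collected prior to or on Study Day 1".

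**The concern.** The rule is built to depend on baseline, but it sets a threshold for only one class of baseline. Because all criteria must be met, a missing threshold does not loosen the rule for the other class; it switches the rule off. The same joint enzyme and bilirubin result then leads to different required action depending on where the subject started.

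Three things hang on 6.3.1: the automatic permanent stop, the absolute rechallenge bar in 6.3.3, and the Appendix A requirement to report joint elevation as a serious adverse event within 24 hours. The last refers to the criteria of Section 6.3, and the only criterion there that joins enzymes with TBL or INR is 6.3.1. Without it, Appendix A falls back on the general seriousness definition. No reason is given for leaving out raised baselines, and the neighbouring table in 6.3.2 leaves none out.

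**Working it through.** The plan gives no figure to reproduce here. The check applies the stated rules to eligible subjects.

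**1. Which baseline applies.** The protocol does not define baseline for this rule. Screening chemistry is the only chemistry scheduled before dosing, so the screening value normally serves, with or without the SAP definition. Eligible AST and ALT are each below 3x ULN.

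**2. Who can meet 6.3.1.** Take the no-other-cause criterion as met. As printed, the rule is: (TBL > 2x or INR > 1.5) and [(baseline AST < ULN and AST > 3x) or (baseline ALT < ULN and ALT > 3x)].

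The grid used 9 on-study values for each enzyme (2.5x to 10x ULN, 7 of them above 3x), 5 TBL values (1x to 3.5x ULN) and 2 INR values (1.0, 1.6). That is 9 × 9 × 5 × 2 = 810 on-study combinations per baseline pair. The TBL/INR limb is met in 8 of its 10 combinations.

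| Baseline | Pairs | Combinations | Meet 6.3.1 as printed | Meet it with an 'Any' row |
|---|---|---|---|---|
| Both < ULN | 4 | 3,240 | 4 × 77 × 8 = 2,464 | 2,464 |
| One ≥ ULN | 16 | 12,960 | 16 × 63 × 8 = 8,064 | 16 × 77 × 8 = 9,856 |
| Both ≥ ULN | 16 | 12,960 | 0 | 9,856 |

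Here 77 = 81 − 4 enzyme pairs have at least one value above 3x, and 63 = 7 × 9 have the enzyme that was normal at baseline above 3x. These are counts of rule outcomes, not patient frequencies. With both enzymes raised at baseline, no on-study result meets the rule. With one raised, the rule still works through the other.

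**3. What 6.3.2 adds.** Eight illustrative states, with AST = ALT on study, ALP normal, monitoring kept and no other cause. Unless stated, TBL is 2.5x ULN and there are no symptoms. 'Judgement' means that neither section requires stopping or withholding, so the safeguards discussed under the objection govern.

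| State | Baseline 0.9/0.9x | Baseline 2.0/2.0x, as printed | 2.0/2.0x, 'Any' row |
|---|---|---|---|
| 4.5x, day 1 | permanent | judgement | permanent |
| 4.5x, day 28 | permanent | judgement | permanent |
| 4.5x, TBL 1.0x, INR 1.6, day 1 | permanent | judgement | permanent |
| 7x, day 7 | permanent | judgement | permanent |
| 7x, day 14 | permanent | withhold | permanent |
| 8.5x | permanent | withhold | permanent |
| 4.5x, TBL 3.1x | permanent | withhold | permanent |
| 4.5x, hepatitis symptoms | permanent | withhold | permanent |

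Baseline 0.9/2.0x behaves like 0.9/0.9x in all eight.

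**4. The zone where neither section requires action on dosing.** Both enzymes at or above ULN at baseline, and on study:
- AST/ALT above 3x and up to 5x ULN, or above 5x and below 8x ULN for under 2 weeks with monitoring kept;
- TBL above 2x and up to 3x ULN, or INR above 1.5 with TBL no higher than 3x ULN;
- ALP no higher than 8x ULN, no hepatitis symptoms, no other apparent cause.

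Table 3 limits INR testing to DILI follow-up, so the INR route arises only in a subject already being followed.

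**5. Effect of an 'Any' row on the enzyme rise needed.** Fold rise to pass 3x ULN = 3 / baseline: 3.0 at 1.0x, 2.0 at 1.5x, 1.5 at 2.0x, 1.2 at 2.5x and 3 / 2.9 = 1.03 at 2.9x ULN.

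**The case against.** A reader might infer that these subjects are unprotected, or that dosing simply continues. The documents do not support that. The closing paragraph of 6.3.1 arguably covers them and asks for an investigator decision with immediate medical-monitor contact. Section 6.2.1.2 says that if the investigator or medical monitor considers laboratory changes a significant health risk, "dosing of an individual subject should be stopped and not resumed". Appendix A requires close observation for any AST or ALT above 3x ULN whatever the baseline, with retesting every 24 hours while TBL exceeds 2x ULN or INR exceeds 1.5 (less often once values stabilize in a subject without symptoms), and a hepatology consult. Section 8.2 lets the investigator or sponsor withdraw a subject from the drug at any time, and the DMC sees unblinded data about monthly. Withheld subjects have no stated route back unless another cause is found and values resolve, and 6.3.3 then needs unanimous agreement. All of this stands. It limits the harm, but it monitors or relies on judgement and does not replace the automatic stop.

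The contrast in the table of eight states assumes no other cause. Section 6.3.1 lists right-sided heart failure, hypotension and fatty liver disease among the alternatives, and a heart-failure subject with raised enzymes before dosing may well have one. The case would then go to judgement even under a corrected table, so the fix would change fewer cases than the table suggests. That also stands.

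The one-row table may be an artefact of reading the PDF. The four-row table in 6.3.2 came through intact, which makes a lost row less likely but does not exclude it. Finally, leaving chronically raised enzymes to judgement can be defended as a choice, but the protocol does not say that it made one.

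**Conclusion.** The point holds as a minor drafting gap in a safety rule, provided the source table really has one row. For an eligible subject with both enzymes at or above ULN at baseline, the automatic permanent stop, the absolute rechallenge bar and the automatic joint-elevation report cannot apply, whatever the on-study values. In the narrower zone of step 4, withholding is not required either.

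Two wider readings go too far. A single raised enzyme does not disable the rule. Nor can the point be turned into a number of subjects, because the documents give no share with both enzymes raised at baseline and no rate of joint elevation. With close observation and medical-monitor contact in place, the practical risk is small. Endpoints, sample size and planned analyses are unaffected.

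**What to change.** First check the table in 6.3.1 against the source protocol. If it has one row, amend that row to apply to any baseline, matching 6.3.2. Keep the threshold above 3x ULN with an increase from baseline, and keep the existing TBL/INR and no-other-cause conditions. This restores all three consequences of 6.3.1 together. It also lets a subject with one raised enzyme qualify through that enzyme. If the sponsor's clinicians think 3x ULN too low for raised baselines, a separate row for baseline at or above ULN with their own threshold would also close the gap.

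The change needs one table row in a protocol amendment and no extra visits, samples or procedures. Its downside is that a subject already close to 3x ULN could occasionally be stopped permanently on a small enzyme rise, although the bilirubin or INR rise and the absence of another cause would still be required.
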